4 STUDY POPULATION

Randomized Controlled Trial In a systematic review, patient navigation was associated with a 15% improvement over standard of care for completion of primary colorectal cancer screening, with the proportion of participants who complete screening after navigation ranging from 27-67%. As the degree to which HPV and colorectal screening are analogous is unknown, we chose to err on the conservative side and, in order to ensure adequate power, based our calculations on the assumption that at least a 6% difference exists between screening non-attendees who complete mailed self-sample HPV testing with patient navigation compared to those who complete the self-sample testing without patient navigation. With 756 participants in each study arm and a total of 2,268 (nQueryAdvisor version 7.0), we can expect to detect the indicated differences in proportions between Arms 2 and 3. Given the large numbers of screening non-attendees enrolled in Harris Health (>15,000), we anticipate that we will be able to accrue this number of participants over a period of 30 months, with completion of follow-up in 36 months.

The sample size has been revised to account for an additional 240 Asian/Asian American women who will be enrolled as part of an administrative supplement. For the Asian/Asian American targeted enrollment study, the estimated number of participants who can be enrolled in a six month period with the two patient navigators who will remain on the team is 240. A recent meta-analysis of trials showed a pooled 12.8% improvement in intent-to-treat analyses measuring screening uptake in mail-to-all self-sample HPV testing

compared to usual care (4). Using this data, our sample size of 240 (120 in Arm 1, 60 each in Arms 2 and 3) provides 85.2% power to detect an improvement of 12.8% between usual care (Arm 1) and mailed self-sampling (Arms 2 and 3 combined) with alpha=0.05 (30).

Telephone Survey The sample size is designed to assess the main effect of patient navigation on reported barriers to self-sampling. Specifically, it is designed to detect a 25% difference in the proportion of participants who report one of the top three barriers reported in our previous research (concerns of injury, safety, and cleanliness), comparing women who did and did not receive patient navigation. Specifying an expected proportion of 0.30, 80% power, and $\alpha=0.05$, the target sample size is 272 (n=68 in each group of the factorial design).

For the Asian/Asian American targeted enrollment study, we will conduct an additional 40 telephone surveys among a random sample of Asian/Asian American participants in the self-sampling arms (Arms 2 and 3) who do (n=20) and do not (n=20) return their self-sampling kit.

Qualitative Interviews We will invite 15 HR-HPV positive women who attend and 15 who do not attend for clinical follow-up within 6 months of their test results. Based on our pilot data, we estimate that this number of participants will be sufficient to reach data saturation (i.e., redundancy in results to the point where additional interviews do not provide new information) and allow us to identify themes and trends in the data. Participants will be purposively selected to attain a demographically diverse sample.

We will conduct 10 semi-structured telephone interviews with 10 Asian/American participants who complete self-sample HPV testing and who test positive for HR-HPV to identify reactions to a positive test and attitudes and barriers to clinical follow-up.

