2 OBJECTIVES

2.1 Primary Objectives

The overall purpose of this protocol is to evaluate the effectiveness of self-sample HPV testing with patient navigation to increase cervical cancer screening among women who otherwise do not regularly attend for clinic-based screening (i.e., Pap test).

The specific aims of this protocol are to: SPECIFIC AIM 1: Compare the effectiveness of mailed self-sample HPV testing alone and in combination with patient navigation to increase primary screening participation (primary outcome) and clinical follow-up (secondary outcome).

Hypothesis 1.1: Primary screening participation and clinical follow-up will be significantly greater among women randomized to receive telephone recall with mailed self-sampling kits versus telephone recall alone. Hypothesis 1.2: There will be significant incremental gains in screening participation and clinical follow-up among women randomized to receive mailed self-sampling kits in combination with patient navigation.

After receiving an administrative supplement, we have revised the trial to include Asian/Asian American women who are currently under-presented in the trial and in the broader literature on self-sampling. In doing so, we will ensure that the trial is powered to rigorously assess and compare screening participation and other outcomes across racial/ethnic and linguistic subpopulations inclusive of Asian/Asian American women. Collectively, the data generated in pursuit of these aims and those of the larger trial will define the impact of mailed self-sample HPV testing among medically underserved Asian/Asian American and other racial/ethnic minority women in safety net health system settings.

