3 STUDY METHODS

3.1 Study Methods

Eligible women will be identified monthly through a query of the EMR database. Data will be extracted and transferred to OnCore (Forte Research Systems, Madison, WI) for randomization, storage, and data management. A computer-generated permuted block randomization scheme will be used to randomly assign individuals to the three trial arms with a 1:1:1 ratio using participants' medical record number. Randomized women will receive a study-specific identification number. Randomized women will be contacted by telephone. Those who are not reached will be contacted on 3 different days at 3 different times before being classified as unreachable. Unreachable participants will be replaced by randomly-selecting additional eligible women until the target sample size is met. Women who hang up the telephone before the scripted message is delivered will receive a second call within 10-30 minutes. Those who do not hear the full message on the second attempt will be categorized as refusers.

The 3 arms of the RCT are: Arm 1: Telephone recall (control). Participants will receive a scripted telephone recall from a trained patient navigator (PN) on behalf of Harris Health. Arm 2: Telephone recall with mailed HPV self-sampling kit (intervention). Participants in this arm will receive a scripted telephone recall from a PN on behalf of Harris Health and receive a mailed HPV self-sampling kit with a pre-paid return envelope.

Arm 3: Telephone recall with mailed HPV self-sampling kit and patient navigation (intervention plus). Participants in this arm will receive the same scripted telephone recall and mailed self-sampling kit as in Arm 2. Within 3-5 days of the kit's mail-out, participants will receive a telephone call from the PN.

Procedures for the three arms of the RCT are as follows:

Arm 1: Telephone recall (control). Participants will receive a scripted telephone recall from a trained patient navigator (PN) on behalf of Harris Health. PNs will let the patient know of the telehealth options available to Harris Health patients during the COVID-19 pandemic. Patients will be given the contact information for the call center that can walk them through the steps of accessing telehealth. PNs will also inform participants that their records indicate that they are overdue for a Pap test and that primary care, including well woman exams and Pap testing is still important during the pandemic.

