4.2 Exclusion Criteria

Randomized Controlled Trial Patients who self-pay will be excluded unless they were covered under a Harris Health healthcare coverage plan within the past 12 months. This is to ensure that all participants are able to receive follow-up clinical care from Harris Health System, as needed. For those with expired eligibility, expedited emergency coverage can be instituted as needed, per a process worked out with Harris Health System financial assistance leadership. Additional exclusion criteria will be assessed by chart review and at the time of attempted telephone contact. Specifically, we will exclude women who lack valid telephone contact information; are unable to communicate in English, Spanish, Vietnamese or other Asian language where translation services are available; or self-report being currently pregnant.

Telephone Survey Women who test positive for HR-HPV and require clinical follow-up are not eligible for the survey.

Qualitative Interviews Women who test negative for HR-HPV are not eligible for the qualitative interviews.

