We request not to require signing the form, because we fear that it will introduce significant bias into our research. Instead we have included language in both the letter and the information sheet that makes it clear to participants that their completion and return of the self-sampling kit indicates their consent to participate.

Finally, none of the subjects are being compensated for their participation in this study, so there is no financial influence in participant's decision to take part in the study.

The introductory letter and research information sheet are available in English and Spanish. Both versions are attached in Section S.

Telephone Survey Women who are randomly selected to participate in the telephone survey and women who are selected to participate in the qualitative interviews will be contacted by telephone by a trained, bilingual research assistant and invited to participate in the survey. The informed consent will be read to participants, emphasizing voluntary nature of the study and that participation will not affect their participation in the larger RCT or their ability to obtain healthcare services at Harris Health. Women will be given the opportunity to ask questions. After doing so, they will be asked to verbally indicate whether they agree to participate in the survey/interview.

Consent and Enrollment of Vietnamese-speaking Subjects See attachment, file name: "209230 - Baylor College of Medicine_COA" for certificate of translation of Vietnamese-language materials. See attachment, file name: "Consent and Enrollment of Vietnamese-speaking Subjects".

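### The supplement's 85.2% power assumes a 120/60/60 split, but the only stated randomisation rule is 1:1:1, and the Arm 1 rate behind the figure is not given

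*Combined protocol and SAP*

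**What the plan says.** Section 4 (Study Population) adds 240 Asian/Asian American women to a parent trial of 756 per arm (2,268 in total). The 240 is a capacity figure: "the estimated number of participants who can be enrolled in a six month period with the two patient navigators". The power statement is "our sample size of 240 (120 in Arm 1, 60 each in Arms 2 and 3) provides 85.2% power". The contrast is Arm 1 against the two self-sampling arms taken together, for a gain of 12.8% at an alpha of 0.05. The 12.8% is attributed to a meta-analysis. No screening rate is printed for Arm 1 or for the self-sampling arms, and alpha is not described as one- or two-sided.

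Section 3.1 says a permuted-block scheme "will be used to randomly assign individuals to the three trial arms with a 1:1:1 ratio". The same sentence appears in 4.4, 6.2 and 6.2.1. None of the four places mentions a different ratio or a separate list for the supplement.

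Parts of the plan were revised for the supplement. Sections 4.4, 6.2 and 6.2.1 each carry a pointer, "Consent and Enrollment of Vietnamese-speaking Subjects See attachment", and section 4.2 now excludes only women who "are unable to communicate in English, Spanish, Vietnamese or other Asian language where translation services are available".

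On the analysis, section 2.1 says "we have revised the trial to include Asian/Asian American women". Section 4 treats the same women as a study with its own contrast and its own survey sample: "For the Asian/Asian American targeted enrollment study, we will conduct an additional 40 telephone surveys". Section 3.4 compares Arms 1, 2 and 3 with Pearson chi-square tests and log binomial regression, without saying whether the supplement women are included.

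**The concern.** The power statement and the randomisation rule describe different designs. A 120/60/60 split is 2:1:1; the stated rule is 1:1:1. Someone building the supplement's list from the visible text would produce about 80/80/80, and the powered contrast would be 80 against 160, which the 85.2% does not describe.

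Because the Arm 1 rate is missing, a reader can neither reproduce the 85.2% nor work out what it becomes under 1:1:1.

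The ratio also bears on the analysis. If the women are pooled with the parent trial at 2:1:1, cohort membership is associated with arm and the Arm 1 contrasts are no longer balanced by cohort. At 1:1:1 that problem does not arise. So the ratio and the supplement's place in the primary analysis have to be settled together.

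**Working it through.** **Inputs from section 4:** total 240; split 120/60/60; improvement 12.8%; alpha 0.05; stated power 85.2%. **From section 3.1:** ratio 1:1:1, hence 240/3 = 80 per arm (inferred, not printed). **From section 3.4:** Pearson chi-square as the test.

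**Assumptions:** the 12.8% is an absolute difference (d = 0.128); alpha is two-sided unless noted; the Arm 1 rate p1 is unknown, so it is solved for or shown as a range. p2 = p1 + 0.128.

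**Formulas.** Let SE0 = √[p̄(1−p̄)(1/n1 + 1/n2)], with p̄ the rate weighted by sample size, and SE1 = √[p1(1−p1)/n1 + p2(1−p2)/n2].
- Pooled: power = Φ[(d − 1.960·SE0)/SE1]
- Unpooled: power = Φ[d/SE1 − 1.960]
- Exact Pearson: the sum of binomial probabilities over all tables that the test rejects

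**Step 1: reproduce 85.2% at 120 against 120.** This cannot be done directly without p1. Solving the pooled formula gives p1 = 0.0622:
- p̄ = 0.1262, SE0 = 0.04287, SE1 = 0.04207
- (0.128 − 1.960 × 0.04287)/0.04207 = 1.045, and Φ(1.045) = 0.852

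The stated figure is therefore attainable, but only at a low Arm 1 rate that is not printed.

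**Step 2: same rate, 80 against 160.**
- p̄ = 0.1476, SE0 = 0.04856, SE1 = 0.04114
- (0.128 − 1.960 × 0.04856)/0.04114 = 0.798, and Φ(0.798) = 0.787

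**Step 3: other methods, each solved to give 85.2% at 120 against 120.**

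| Method | Arm 1 rate needed | Power at 80 vs 160 |
|---|---|---|
| Pooled, two-sided | 6.2% | 78.7% |
| Exact Pearson, two-sided | 6.8% | 78.7% |
| Unpooled, two-sided | 6.6% | 86.5% |
| Pooled, one-sided | 10.1% | 80.4% |

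The unpooled formula shows no loss because moving women into the arms with the higher rate, and so the higher variance, lowers SE1 slightly, and that formula ignores SE0. At its own rate of 6.6%, the exact power of the planned Pearson test still falls, from 85.9% to 79.5%.

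**Step 4: sensitivity to the unstated rate (pooled, two-sided; all rates assumed).**

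| Assumed Arm 1 rate | 120 vs 120 | 80 vs 160 |
|---|---|---|
| 5% | 88.2% | 82.4% |
| 10% | 76.7% | 69.2% |
| 15% | 67.8% | 60.5% |
| 20% | 61.5% | 54.7% |

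Reading down a column shows the effect of the missing rate. Reading across a row shows the effect of the allocation, about 6 to 7 points.

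**Step 5: cohort balance if pooled with the parent trial.**
- At 2:1:1: Arm 1 120/(756 + 120) = 13.7% supplement women; Arms 2 and 3 each 60/(756 + 60) = 7.4%. The gap is 6.3 percentage points, so a 10-point difference in screening rate between cohorts would shift a crude Arm 1 contrast by 0.0635 × 10 ≈ 0.63 points, in either direction.
- At 1:1:1: 80/(756 + 80) = 9.6% in every arm, so there is no imbalance.

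**The case against.** The strongest reply is that the specific statement governs. Section 4 is the only place that gives arm sizes for the supplement, and it is explicit. The 1:1:1 sentence fits the parent design and may simply not have been revised. Other parent wording clearly was not: section 1.2 still describes eligibility as limited to English and Spanish speakers, and 4.4 still lists the letter and information sheet in those two languages only. The study schema and the attachment on enrolling Vietnamese-speaking women are not shown, and either could contain a 2:1:1 scheme. On this reading the defect is a missing sentence in the randomisation text and the power figure is sound.

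Much of this stands. It is a plausible account of how the conflict arose, and it is why the claim is confined to the visible text. It does not remove the conflict: the rule is printed four times without qualification, three of those sections were edited for the supplement, and section 2.1 says the trial itself was revised to include these women.

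It is also fair that the size of the loss depends on the formula and the sidedness, that assumed rates of 10% and above cannot underlie a two-sided 85.2%, and that the pooling issue is conditional and probably small. The missing rate is a reporting gap and no proof of miscalculation.

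**Conclusion.** The concern holds and should be fixed. In the visible text, the stated power rests on a 2:1:1 split that the only stated randomisation rule does not produce.

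If 1:1:1 is applied, power for the Arm 1 contrast falls by roughly 6 to 7 points under the pooled and exact two-sided calculations (85.2% to 78.7%), by about 5 points under a one-sided pooled calculation (to 80.4%), and not at all under the unpooled formula. These figures assume that the 12.8% is an absolute difference and that the Arm 1 rate is the one that returns 85.2% under each method.

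If 120/60/60 is applied, the 85.2% may be correct but cannot be verified without the Arm 1 rate. The total of 240 is unaffected either way, since navigator capacity sets it. Any bias from pooling at 2:1:1 is of unknown direction and likely modest.

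**What to change.** Reconcile section 4 with sections 3.1, 4.4, 6.2 and 6.2.1 in one of two ways:

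- **(a)** State in all four randomisation passages that the 240 supplement participants are allocated 2:1:1 (120/60/60), for example from a separate permuted-block list.
- **(b)** Keep 1:1:1 for everyone and restate the supplement's power for 80 against 160.

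In either case, print the Arm 1 rate used, name the test or formula, and confirm that alpha 0.05 is two-sided. State in sections 3.4 and 4 whether the supplement women enter the primary comparison of Arms 1, 2 and 3 or are analysed separately.

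Only if they are pooled at 2:1:1, stratify the Arm 1 contrasts by cohort (parent or supplement), with a Cochran-Mantel-Haenszel test and a cohort term in the log binomial model.

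The cost is wording: one sentence repeated in four places, a few lines in the sample-size and analysis sections, and one stratification factor in the conditional case. Under (b) the stated power may be lower. No extra participants are required.

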3.4 Data Analysis

Randomized Controlled Trial Primary outcome. Primary screening participation will be examined dichotomously (screened/not screened) using an "intent-to-screen" analytic approach. Bivariable tables and Pearson's χ^2 tests will be used to compare the proportion of primary screening participation across Arms 1, 2, and 3, as well as the absolute difference in participation across Arms 1, 2 and 3. Bivariable tables and Pearson's χ^2 tests will be used to compare the proportion of primary screening participation by study arm, as well as the absolute difference in participation across arms. Log binomial regression will be used to calculate the relative risks of primary screening participation and corresponding 95% confidence intervals (CIs). Secondary outcomes. Descriptive analyses of secondary outcomes will be conducted using bivariable tables and Fisher's exact tests to describe and compare test results and attendance for clinical follow-up across study arms 1, 2 and 3. Log binomial regression will be used to calculate relative risks and 95% CIs of having a positive screening test and of attending for clinical follow-up.

Analytic sub-aim: 1) We will use descriptive statistics (bivariable tables and chi-square/Fisher's exact tests) to compare characteristics of un/under-screened women and those who are up-to-date on screening across Arms 1, 2, and 3. Multivariable logistic regression will be used to assess the independent association between screening status and participant characteristics. 2) Detection and treatment of precancers will be explored through descriptive analyses using bivariable tables and Fisher's exact tests. 3) Among participants in Arms 1, 2 and 3, we will conduct separate analyses to assess characteristics associated with primary screening participation. For Arms 1, 2 and 3, we will use bivariable tables with Pearson's χ^2 tests to describe characteristics of screened and unscreened participants. Characteristics of interest include age, race/ethnicity, months since last Pap test, health plan type, number of healthcare encounters in the past 12 months, and time enrolled as a Harris Health patient. Associations with $p<0.10$ will be used to determine candidate variables for subsequent multivariable

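### Section 4 powers the Asian/Asian American supplement on Arm 1 versus Arms 2 and 3 combined, but Section 3.4 carries over neither that contrast nor any arm comparison within this group

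*Combined protocol and SAP*

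**What the plan says.** Section 4 (Study Population) sizes the supplement on one comparison. The effect comes from an outside source: "A recent meta-analysis of trials showed a pooled 12.8% improvement in intent-to-treat analyses measuring screening uptake in mail-to-all self-sample HPV testing" compared with usual care. The allocation is "our sample size of 240 (120 in Arm 1, 60 each in Arms 2 and 3", and the claim is that this "provides 85.2% power to detect an improvement of 12.8% between usual care (Arm 1) and mailed self-sampling (Arms 2 and 3 combined", with alpha 0.05. No Arm 1 screening rate is given, and alpha is not said to be one- or two-sided.

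Section 3.4 (Data Analysis) gives the primary-outcome analysis for the trial. Pearson chi-square tests will "compare the proportion of primary screening participation across Arms 1, 2, and 3, as well as the absolute difference in participation" across those arms, and "Log binomial regression will be used to calculate the relative risks of primary screening participation and corresponding 95% confidence intervals". No reference arm or pairwise contrast is named, and Arms 2 and 3 are never pooled. In the trial analyses of that section, race/ethnicity is named only in sub-aim 3, as a possible correlate of being screened: "Characteristics of interest include age, race/ethnicity, months since last Pap test" and so on.

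Section 2.1 says that the supplement will leave the trial powered to assess and compare screening participation across racial/ethnic and linguistic subpopulations, Asian/Asian American women included. Section 1.2 gives the reason for it: there were too few such women for subgroup analysis.

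**The concern.** The supplement exists to answer a question in Asian/Asian American women, and its size is justified by one pooled contrast in them. The section that fixes the analyses contains neither the population nor the contrast. Someone working from Section 3.4 alone would either make no arm comparison in this group or apply the three-arm methods to it.

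Two things are at stake. First, the three-arm and single-arm tests have less power in these 240 women than the pooled contrast does, so a real kit effect is more likely to be missed than Section 4 implies. Second, pooled, three-arm and pairwise tests all remain open, so the choice among them could be made after the data are seen.

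**Working it through.** **Inputs.** From Section 4: 120/60/60 women, a difference of 12.8%, alpha 0.05, stated power 85.2%. Assumed, because the documents are silent: the 12.8% is in absolute percentage points, the test is two-sided (z = 1.96), and both kit arms have the same rate p2 = p1 + 0.128. The Arm 1 rate p1 is unknown and is varied.

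**Formulas.** Two groups: power = Φ[(|p2 − p1| − z·s0)/s1], with s0 = √[p̄(1 − p̄)(1/n1 + 1/n2)] and s1 = √[p1(1 − p1)/n1 + p2(1 − p2)/n2], where p̄ is the overall rate. Three arms: noncentral chi-square on 2 df with λ = Σ n_i(p_i − p̄)²/[p̄(1 − p̄)] and critical value 5.99.

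**Step 1: reproduce 85.2%.** Solving for p1 gives about 6.2%. At 6.2% v 19.0% with 120 v 120: p̄ = 0.126, s0 = 0.0428, s1 = 0.0420. Then (0.128 − 1.96 × 0.0428)/0.0420 = 1.05, and Φ = 0.85. This solution is not unique: a one-sided 0.05 test at p1 = 10% also gives 85.3%.

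**Step 2: one kit arm v Arm 1 (60 v 120), same rates.** p̄ = (120 × 0.062 + 60 × 0.190)/180 = 0.105, s0 = 0.0484, s1 = 0.0552. Then (0.128 − 1.96 × 0.0484)/0.0552 = 0.60, and Φ = 0.73.

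**Step 3: three-arm test (120/60/60), same rates.** λ = 240 × 0.064²/(0.126 × 0.874) = 8.93, and power on 2 df = 0.77. With equal kit arms, splitting them costs a degree of freedom and adds nothing to λ.

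**Step 4: vary the Arm 1 rate.** The first figure is from the formulas. The second is from exact binomial enumeration of the chi-square test (two groups) or simulation (three arms).

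| Arm 1 rate | Combined, 120 v 120 | Three-arm, 2 df | One kit arm v Arm 1 |
|---|---|---|---|
| 5% | 88% / 90% | 80% / 84% | 76% / 79% |
| 6.2% | 85% / 87% | 77% / 80% | 73% / 75% |
| 10% | 77% / 78% | 67% / 69% | 63% / 63% |
| 20% | 62% / 62% | 51% / 52% | 47% / 48% |

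**Step 5: unequal kit arms.** Suppose the effects are 9.8 and 15.8 points, which average 12.8 and differ by the 6 points that Section 4 assumes for navigation in the main trial. At p1 = 6.2%, simulation gives about 83% for the three-arm test against 87% for the combined contrast. By the Step 2 formula, Arm 3 v Arm 1 has about 85% and Arm 2 v Arm 1 about 56%.

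**Step 6: allocation.** Sections 3.1, 4.4, 6.2 and 6.2.1 all state 1:1:1 randomisation; 120/60/60 is 2:1:1. At 80/80/80 and p1 = 6.2% the combined contrast is 80 v 160: p̄ = 0.147, s0 = 0.0485, s1 = 0.0411. Then (0.128 − 1.96 × 0.0485)/0.0411 = 0.80, and Φ = 0.79.

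**The case against.** The strongest reply is that this is a single combined document, and Section 4 already names the group, the contrast, the effect and alpha. A fair reader would take that as the intended comparison rather than put a three-arm test in its place. This stands to the extent that the plan cannot be said to lack the contrast altogether. But a sample-size sentence does not fix the test, the effect measure or the standing of the arm-specific results, and Section 3.4, which should, is silent.

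A reader might go further and infer that the planned tests deliver only 73-77% power. The documents do not support that, for four reasons:

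- Section 3.4 plans no test confined to Asian/Asian American women. Its tests cover the whole trial (756 per arm plus the supplement), and 73-77% is not their power. It describes those methods applied hypothetically to the 240 women alone.
- The figure needs an Arm 1 rate and a sidedness that the documents do not give.
- It assumes equal kit-arm effects. With unequal effects the three-arm loss is only about 4 points (Step 5).
- The 60 v 120 comparison is itself an inference, since Section 3.4 names no pairwise contrasts.

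It can also be said that the 240 women are additional. Section 1.2 puts Asian/Asian American women at 4% of participants before the supplement. If that held for all 2,268 (0.04 × 2,268 ≈ 91, about 30 per arm) and those women were included, the arms would be 150/90/90. At 6.2%, one kit arm v Arm 1 would then have about 84% and the three-arm test about 88% (91% by simulation), against about 94% for the combined contrast. The levels rise but the ordering does not change. Whether those women would be included is not stated.

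**Conclusion.** The concern holds as a gap between two sections: the population and contrast that justify the supplement in Section 4 are missing from Section 3.4. That conclusion rests on the text alone.

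The size is conditional. With a two-sided 0.05 test, a 12.8-point absolute effect shared equally by both kit arms, and only the 240 women, the three-arm test loses about 6 to 11 points of power against the combined contrast and a single kit arm about 11 to 15, over Arm 1 rates of 5% to 20%. At 6.2% the chance of missing the effect goes from about 15% to 23% (three-arm) or 27% (one kit arm) by the formulas. With enumeration or simulation it goes from 13% to 20% or 25%. None of these is a figure from the documents.

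Separately, the 120/60/60 split and the 1:1:1 randomisation cannot both describe the supplement, and the difference moves the stated power itself by about 6 points at a 6.2% Arm 1 rate. This is worth correcting but does not threaten the main trial.

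**What to change.** Add to Section 3.4: *In Asian/Asian American women, the main analysis compares primary screening participation in Arm 1 with Arms 2 and 3 combined (chi-square test, two-sided 0.05; risk difference and relative risk with 95% CI). Arm-specific results and Arm 2 versus Arm 3 in this group are descriptive.* Say also whether Asian/Asian American women enrolled before the supplement are included.

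In Section 4, state that 85.2% applies to this contrast only, and give the assumed Arm 1 rate and the sidedness. If the figure was one-sided (Arm 1 rate about 10%), restate it for the two-sided test; it would be about 77%.

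Reconcile the 120/60/60 split in Section 4 with the 1:1:1 ratio in Sections 3.1, 4.4, 6.2 and 6.2.1, and recompute the power for whichever allocation applies.

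The cost is one paragraph and a few edits, with no added participants or procedures. The downside is that the navigation increment in this group is openly labelled descriptive. Little is lost: with 60 v 60, a 6-point difference has only about 11-13% power for Arm 2 rates of 15% to 25%, and the documents claim none for it.
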